12.1.1 Ibrexafungerp Monotherapy for All Fungal Diseases, Excluding VVC

Subjects will receive ibrexafungerp monotherapy given as an initial loading dose of 750 mg (3 tablets of 250 mg each) given BID (total daily dose = 1500 mg) during the first 2 days of treatment and then subsequent oral doses of 750 mg (3 tablets of 250 mg each) QD for up to 180 days, depending on fungal disease.

Table 6 Ibrexafungerp Monotherapy Dosing Regimen (Excluding VVC)

	Treatment Days	Ibrexafungerp Dosing Regimen	Total Ibrexafungerp Daily Dose
Loading Dose	Study Days 1 and 2	750 mg BID: 750 mg (3 tablets x 250 mg) AM 750 mg (3 tablets x 250 mg) PM	1500 mg
Maintenance Dose	Study Day 3 to EOT	750 mg QD: 750 mg (3 tablets x 250 mg)	750 mg
██████████	██████████	██████████	██████████

Abbreviations: AM = morning; BID = twice a day; EOT = end of treatment; PM = evening; QD = once a day;
VVC = vulvovaginal candidiasis

Treatment beyond 180 days may be permitted under certain circumstances to be agreed upon by the Investigator and the Sponsor on a per-subject basis. Subjects with a recurrence after TOC (VVC) or EOT (all other diseases) may be considered for re-enrollment upon discussion with the Sponsor.

If subjects cannot swallow the whole tablet, the tablets may be split. In the event subjects experience gastrointestinal intolerance on the 750 mg QD dose, the tablets may be split and/or administered at 10 to 20-minute intervals.

██████████

12.1.2 Ibrexafungerp Monotherapy for VVC

Subjects with VVC will receive ibrexafungerp monotherapy given as oral doses of ██████████

██████████ Subjects treated for VVC who have a recurrence after TOC may receive additional cycles of ibrexafungerp treatment similar to the initial regimen, upon discussion with the sponsor.

Table 7 Ibrexafungerp Monotherapy Dosing Regimen for VVC

Treatment Days	Ibrexafungerp Dosing Regimen	Total Ibrexafungerp Daily Dose
[REDACTED]	[REDACTED]	[REDACTED]
[REDACTED]	[REDACTED]	[REDACTED]
[REDACTED]	[REDACTED]	[REDACTED]

Abbreviations: AM = morning; PM = evening; VVC = vulvovaginal candidiasis

12.1.3 Ibrexafungerp Combination Therapy

Monotherapy with ibrexafungerp is not recommended for refractory or relapsing IPA. All subjects enrolled for refractory or relapsing IPA, mucormycosis or other molds with unpredictable ibrexafungerp activity should receive ibrexafungerp given as combination therapy. Subjects with IPA and intolerance to other SOC options can be considered for enrollment to receive ibrexafungerp monotherapy, upon discussion with the Sponsor.

For subjects who have infections due to other emerging fungi, including yeasts and molds, but have no culture isolate available (to confirm susceptibility to ibrexafungerp), combination therapy should be considered and discussed with the Sponsor. Combination therapy will also be allowed for other subjects based on Investigator's judgement and contingent on Sponsor approval.

Acceptable antifungal therapy includes voriconazole, isavuconazole, posaconazole, fluconazole or amphotericin B (AMB) at the doses recommended per their label. When used in combination with the azoles, the dose of ibrexafungerp should be reduced from 750 mg to 500 mg.

Table 8 Ibrexafungerp – Azole Combination Therapy Dosing Regimen

	Treatment Days	Additional Antifungal	+	Ibrexafungerp Dosing Regimen	Total Ibrexafungerp Daily Dose
Loading Dose	Study Days 1 and 2	Per label	+	500 mg BID: 500 mg (2 tablets x 250 mg) AM 500 mg (2 tablets x 250 mg) PM	1000 mg
Maintenance Dose	Study Day 3 to EOT	Per label	+	500 mg QD: 500 mg (2 tablets x 250 mg)	500 mg

Abbreviations: AM = morning; EOT = end of treatment; PM = evening; QD = once a day

The following combination options are allowed:

- addition of ibrexafungerp to any ongoing antifungal therapy
- replacement of one (toxic/ineffective) element of a two-antifungal combination therapy with ibrexafungerp

- replacement of current monotherapy with a new combination, generally:
 - replacement of AMB monotherapy with an azole plus ibrexafungerp combination, or
 - replacement of an azole monotherapy with an AMB plus ibrexafungerp combination
- continuation of an azole plus echinocandin combination where the subject could go home on an oral regimen by replacing the parenteral echinocandin with ibrexafungerp

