In rats, no new toxicities or target organs of toxicity were identified (compared to experience in shorter terms studies), and the no-observed-adverse-effect-level (NOAEL) was established, which corresponded to mean maximum concentration (C_{max}) and AUC up to the last measurable concentration (AUC_{last}) values on Day 182 of 3290 ng/mL and 73,700 hr·ng/mL in males, and 4060 ng/mL and 87,300 hr·ng/mL in females, respectively. Likewise, in dogs, no new toxicities or target organs of toxicity were identified (compared to experience in shorter terms studies) and the NOAEL was established, which corresponded to mean C_{max} and AUC_{last} values on Day 273 of 1600 ng/mL and 26,700 hr·ng/mL in males, and 2390 ng/mL and 46,100 hr·ng/mL in females, respectively.

Therefore, as no new toxicities were identified following daily oral dose administration to rats and dogs for up to 6 and 9 months, respectively, per ICH M3(R2) dose administration duration in the clinical setting for greater than 6 months is supported.

The *in vitro* studies indicated that ibrexafungerp metabolism was predominantly oxidative, with cytochrome P450 (CYP) 3A being the primary enzyme involved in its oxidative metabolism. Strong inhibitors of CYP3A would be expected to increase plasma levels of ibrexafungerp and its concurrent administration should be avoided.

Clinical experience

To date, the oral formulations of ibrexafungerp have been evaluated in over 1,500 subjects and patients included in multiple Phase 1 and two Phase 2 studies.

Ibrexafungerp was generally well tolerated following single oral doses of up to 1600 mg and multiple oral doses of up to 800 mg/day for 28 consecutive days in Phase 1 studies. Reported adverse events (AEs) after oral administration have been generally transient and primarily mild to moderate in intensity. The most frequently reported AEs have been mild gastrointestinal events (nausea, vomiting, diarrhea and abdominal pain).

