A preliminary efficacy review of the 20 subjects who completed therapy under this study, SCY-078-301, was conducted by an external expert panel (Data Review Committee, DRC). These 20 patients suffered from a variety of conditions, including esophageal candidiasis, intra-abdominal abscesses, spondylodiscitis and oropharyngeal candidiasis, with the most common fungal species being *C. glabrata*, *C. krusei*, and *C. albicans*. Ibrexafungerp treatment ranged from seven to 90 days, with a mean duration of ~37 days. Per DRC evaluation at end of treatment, 11 patients achieved a Complete or Partial Global Response and six patients a stable-disease response. Only two patients showed progression of disease and one patient's outcome was considered indeterminate.

Several drug-drug interaction studies have been conducted. Ketoconazole (a strong inhibitor of CYP3A) induces a significant (5-fold) increase in ibrexafungerp exposure while diltiazem (a moderate inhibitor of CYP3A) induces a mild to moderate (<3 fold) increase in ibrexafungerp exposure. Ibrexafungerp did not have any effect on rosiglitazone (a CYP2C8 substrate) exposure, had only a mild effect (less than a 0.5-fold increase) on the AUC of tacrolimus (a CYP3A and P-gp substrate) and had no effect on the C_{max} of tacrolimus.

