21.2 Appendix B: Prohibited Medications and Medications to be Administered with Caution

21.2.1 Prohibited Medications

No antifungal treatment other than the study drug is allowed during the study except in subject subgroups where combination therapy is allowed or where an exception was granted by the Sponsor on a per-subject basis.

No investigational drugs (i.e., new chemical entities) other than the study drug are allowed within at least 30 days or five and a half half-lives of the investigational product before Screening and throughout the study.

Subjects exposed to prohibited medications may be allowed in the study when treatment options are limited, in discussion with the Sponsor based on a risk-benefit analysis. Additional ibrexafungerp PK and/or therapeutic drug monitoring may be needed in these cases.

Strong CYP3A4/5 inhibitors and CYP3A4/5 inducers

CYP	Strong/Moderate Inhibitors	Inducer ^a
3A4/5	
Reversible inhibitors:^b
 
• boceprevir• conivaptan• indinavir• ketoconazole^c• lopinavir/ritonavir• mibepradil• fluconazole^c• nefazodone• nelfinavir• telaprevir• telithromycin• itraconazole^c• posaconazole^c• voriconazole^c 
Time-dependent inhibitors:^a
 
• clarithromycin• ritonavir• saquinavir	
• avasimibe• carbamazepine• phenytoin• rifampin• St. John's wort

- a. The CYP3A4/5 inducers and strong time-dependent CYP3A4/5 inhibitors listed in this table are not permitted during the 14 days prior to enrollment and during study treatment.
- b. The reversible CYP3A4/5 inhibitors listed in this table are not permitted during 48 hours prior to the administration of ibrexafungerp (except for the antifungal drug administered for the eligible fungal disease), and during the study.
- c. No antifungal treatment other than the study drug is allowed during the study. Fluconazole, itraconazole, posaconazole and voriconazole are prohibited except in subject subgroups where combination therapy is allowed or where an exception was granted by the Sponsor on a per-subject basis.

P-glycoprotein (P-gp) substrates

P-gp Drug Substrate ^a
digoxin, colchicine, vinblastine, talinolol

a. The P-gp substrates listed in this table are not permitted during the administration of ibrexafungerp.

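### The one-third ibrexafungerp reduction with azoles offsets only a 1.5-fold exposure rise, no exposure basis is given for it, and the SAP's safety analysis does not separate the affected subjects

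*Protocol*

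**What the plan says.** Section 12.1.3 lists the permitted partners: "Acceptable antifungal therapy includes voriconazole, isavuconazole, posaconazole, fluconazole or amphotericin B (AMB) at the doses recommended per their label". For the azoles among them it gives a single instruction: "When used in combination with the azoles, the dose of ibrexafungerp should be reduced from 750 mg to 500 mg". Table 8 applies the same reduction to the loading days (1000 mg in place of 1500 mg daily) and to maintenance.

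On interactions, Section 7.1 reports "Ketoconazole (a strong inhibitor of CYP3A) induces a significant (5-fold) increase in ibrexafungerp exposure" and "diltiazem (a moderate inhibitor of CYP3A) induces a mild to moderate (<3 fold) increase in ibrexafungerp exposure". Its nonclinical part says of the class: "Strong inhibitors of CYP3A would be expected to increase plasma levels of ibrexafungerp and its concurrent administration should be avoided".

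Section 13.2 prohibits strong CYP3A4/5 inhibitors, with an exception for antifungals used in permitted combinations or approved by the sponsor for an individual subject. Appendix B (Section 21.2.1) puts fluconazole, posaconazole and voriconazole in the same column as ketoconazole. That column is headed for strong and moderate inhibitors together and does not say which drug is which. A footnote adds: "Fluconazole, itraconazole, posaconazole and voriconazole are prohibited except in subject subgroups where combination therapy is allowed". Isavuconazole, a permitted partner, is not in the table. The synopsis list of partners omits fluconazole.

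Section 7.1 gives NOAEL exposures (mean Cmax and AUClast) for rats, "3290 ng/mL and 73,700 hr·ng/mL in males, and 4060 ng/mL and 87,300 hr·ng/mL in females", and for dogs, "1600 ng/mL and 26,700 hr·ng/mL in males, and 2390 ng/mL and 46,100 hr·ng/mL in females". For the 750 mg regimen in healthy volunteers it gives a Day 7 AUC0-24 of 28 ug.hr/mL.

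SAP Section 8 reports safety for the whole safety population. SAP 6.2.1 and 6.2.2 measure exposure and compliance in number of doses.

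**The concern.** The size of the azole reduction and the size of the reported interactions do not match, and nothing in either document bridges them. Section 7.1 gives simulated and observed exposure for monotherapy only. There is no predicted AUC for the Table 8 regimen, no interaction result for any permitted azole and no derivation of the 500 mg figure.

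Combination therapy is required in refractory or relapsing IPA, mucormycosis and other molds with unpredictable ibrexafungerp activity. Treatment may last 180 days or longer. PK sampling is voluntary and its scheduled samples end by Day 10. Between Screening and EOT, liver tests in non-VVC subjects are done only if clinically indicated.

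If exposure is materially higher with some azoles, the analysis should be able to show any consequence. As the SAP stands, a liver or adverse-event signal confined to azole recipients would be averaged over the whole safety population.

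**Working it through.** **Inputs.** Doses: Section 12.1.3 and Table 8. Interaction ratios, Day 7 AUC0-24 (28 ug.hr/mL) and NOAEL AUCs: Section 7.1, the last converted from hr·ng/mL by dividing by 1000.

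**Step 1: the plan's own reduction.** 500/750 = 0.667 for maintenance and 1000/1500 = 0.667 for loading. Both are a cut of one third. The rise that this exactly offsets is 750/500 = 1.5-fold.

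**Step 2: AUC on 500 mg.** With dose proportionality, AUC = 28 × (500/750) × ratio = 18.7 × ratio. The last four columns give the AUC divided by each NOAEL value.

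| Assumed ratio | AUC (ug.hr/mL) | vs 28 | Dog M 26.7 | Dog F 46.1 | Rat M 73.7 | Rat F 87.3 |
|---|---|---|---|---|---|---|
| 1 | 18.7 | 0.67 | 0.70 | 0.40 | 0.25 | 0.21 |
| 1.5 | 28.0 | 1.00 | 1.05 | 0.61 | 0.38 | 0.32 |
| 2 | 37.3 | 1.33 | 1.40 | 0.81 | 0.51 | 0.43 |
| 3 (ceiling for diltiazem) | 56.0 | 2.00 | 2.10 | 1.21 | 0.76 | 0.64 |
| 5 (ketoconazole) | 93.3 | 3.33 | 3.50 | 2.02 | 1.27 | 1.07 |

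**Step 3: break-even ratios on 500 mg** (NOAEL divided by 18.7): male dog 1.43, female dog 2.47, male rat 3.95, female rat 4.68. All four values are exceeded only above about 4.7-fold.

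**Step 4: reference point.** Monotherapy without an inhibitor: 28/26.7 = 1.05 times the male-dog value. Exceeding that one value is therefore not specific to the combination.

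**Step 5: sensitivity to wording.** If an n-fold increase means n added to the baseline (ratios below 4 and of 6), the two figures become below 74.7 and 112.0.

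**Step 6: what the SAP can see.** Under SAP 6.2.1 a fully compliant subject treated for 180 days takes 2 × 2 + 178 = 182 doses. At 750 mg that is 136,500 mg; at 500 mg it is 91,000 mg. Both subjects show 182 doses and the same compliance. Protocol 18.4.3 calls for data to be presented by receipt of combination therapy (Yes/No), but the SAP carries no such split in efficacy or safety.

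**The case against.** Neither interaction drug is a permitted partner, and no passage classes a permitted azole as strong or gives the size of its interaction. This stands: the 56 and 93 figures show what would follow if the permitted azoles behaved like diltiazem or ketoconazole. They are not predictions. Moreover, 56 is a ceiling, because the diltiazem result is stated only as below 3-fold.

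Section 7.1 and Section 12.1.3 need not be read as rival instructions. The caution in 7.1 is general and follows from in vitro work, while Section 13.2 and Appendix B give an express exemption. This also largely stands. Which instruction governs is mostly clear; what is missing is the exposure reasoning behind it.

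There are safeguards. The sponsor approves each enrolment, and liver events of clinical interest must be reported. Extra PK samples are taken when clinically indicated, and a concentration sample is sought for related severe or serious events. Appendix B says additional monitoring may be needed for subjects on prohibited drugs. These limit the risk to the individual, but they do not supply an exposure figure or separate the subjects in the analysis.

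Section 7.1 refers to the Investigator's Brochure, which may hold the basis for 500 mg. If so, a citation closes that part.

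A reader might also infer that IPA combination subjects as a group have the highest exposure in the trial. The documents do not support that. Amphotericin B is a permitted partner and lies outside the Table 8 regimen, and among azole recipients the inference needs a rise above 1.5-fold.

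**Conclusion.** The point holds as a gap in justification and in analysis. The reduction offsets a 1.5-fold rise, and the protocol's only interaction figures are below 3-fold and 5-fold. Extrapolated to the permitted azoles, AUC on 500 mg would be at most about 56 ug.hr/mL for a moderate inhibitor, above both dog NOAELs and below both rat values. For a strong one it would be about 93, above all four.

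This rests on dose proportionality, on healthy-volunteer AUC0-24 being comparable with animal AUClast, on reading n-fold as a ratio of n, and on the permitted azoles resembling the drugs tested. Only AUC can be compared, since no human Cmax is given for this regimen.

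It would be tempting to conclude that azole-combination subjects are dosed above toxic exposure. The documents do not show that. Exceeding a NOAEL means the margin is gone, not that harm occurs, and monotherapy already exceeds the lowest value by 5%. The point concerns azole combinations only. It merits correction but is not a must-fix.

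**What to change.** **Protocol.** Reconcile Sections 7.1, 12.1.3 with Table 8, 13.2 and 21.2.1, and align the synopsis partner list with 12.1.3. Say how each permitted azole, including isavuconazole, is classed as a CYP3A inhibitor. Give the exposure basis for the azole rule, or cite the document that holds it. This review does not say which dose or clinical rule is right.

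**SAP Section 8.** Tabulate TEAEs, SAEs and liver events of clinical interest for azole-combination subjects beside all others. Keep amphotericin B combinations out of the azole column.

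**SAP 6.2.** Summarise exposure in mg as well as in doses. This also brings the SAP closer to the presentation by combination therapy in Protocol 18.4.3.

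**Cost.** Some protocol wording or a citation, one derived exposure variable and one extra table column. The column will hold small numbers and should be read descriptively. If the exposure basis is not already held, producing it may take more work, because the protocol does not say whether the existing population PK model covers azole interactions.

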12.1.4 Dietary Requirements

Oral study drug should be taken with approximately 8 oz/240 mL of water, preferably with food. For subjects on continuous feeding via an NG or PEG tube, the drug should be crushed and administered with approximately 8 oz/240 mL of water. The tube should be closed at least one hour before drug administration and should be flushed with approximately 20 mL of water before and after drug administration.

12.2 Study Drugs

12.2.1 Ibrexafungerp Description

Study Drug Identifier: Ibrexafungerp

Empirical Formula: C₅₀H₇₅N₅O₁₁ (citrate salt)

Molecular Weight: 922.18 (citrate salt)

Physical Description: White to off-white solid

Chemical Name: (1S,4aR,6aS,7R,8R,10aR,10bR,12aR,14R,15R)-15-[[2(R)-2-amino-2,3,3-trimethylbutyl]oxy]-8-[(1R)-1,2-dimethylpropyl]-14-[5-(4-pyridinyl)-1H-1,2,4-triazol-1-yl]-1,6,6a,7,8,9,10,10a,10b,11,12,12a-dodecahydro-1,6a,8,10a-tetramethyl-4H-1,4a-propano-2H-phenanthro[1,2-c]pyran-7-carboxylic acid, citrate salt]

[figure not shown]

Figure 2 Chemical Structure of Ibrexafungerp Citrate

12.2.2 Formulation, Packaging and Labelling

Ibrexafungerp citrate drug product for oral administration will be supplied as compressed oral tablets containing 250 mg of ibrexafungerp active ingredient on a free base basis. In addition to the active ingredient, the oral tablet formulation also contains silicified microcrystalline cellulose, crospovidone, mannitol, colloidal silicon dioxide, magnesium stearate (non-bovine), and butylated hydroxyanisole. Ibrexafungerp is packaged in bottles containing 30 tablets.

Labels on the bottles of ibrexafungerp will include information as required by regional regulations and may include:

- Sponsor information
- Protocol number
- Protocol visit number
- Place to write the subject number
- Route of administration
- Lot number
- Product name and potency
- Contents, e.g. number of tablet count per bottle
- Storage conditions
- Name of manufacturer and date of manufacture
- Caution statement according to local regulations: "Caution: New Drug – Limited by Law to Investigational Use Only"

12.2.3 Storage and Stability

The pharmacist or appropriate designee at each clinical research site will be responsible for the study drug. Ibrexafungerp tablets are to be stored at room temperature: between 15°C and 25°C with allowable limited excursions of up to 30°C.

For long-term storage at the site, study drug supplies must be kept in a secure area (e.g., locked cabinet) and stored at room temperature.

The site will be required to keep a temperature log to establish a record of compliance with these storage conditions. All study drug will be kept in a secure cabinet or room with access restricted to necessary clinic personnel.

12.3 Drug Accountability

The Investigator or designee will inventory and acknowledge receipt of all shipments of the study drug. Drug accountability logs will be used to maintain accurate records of receipt, dispensing,

administration to each subject, and return of drug. A study monitor will periodically check the supplies of investigational products held by the site to verify accountability of all study drugs. At the conclusion of the study, after final drug accountability has been completed by the monitor, all unused study drug and all medication containers will be returned to the Sponsor or destroyed on site if the site has procedures in place for study drug destruction.

Drug supplies will be maintained in a secure, limited-access storage area under the recommended storage conditions.

The study drug supplied for this study is only for use in subjects who were properly consented and enrolled under this protocol.

A study site designee (e.g., pharmacist, study nurse/coordinator) will:

- Record the treatment in the drug accountability log.
- Count the number of tablets per bottle before dispensing to subject.
- Report and document any study medication issues such as contamination, crushed or broken tablets, incorrect labelling.
 - All product quality complaints should be reported to the Sponsor.
- Collect and count the number of tablets remaining at the EOT visit.

Review subject diary card and remaining study drug count, record any unused or remaining drug in the drug accountability log and eCRF, and note any discrepancies and reason for discrepancies.

12.4 Subject Compliance with Study Drug Dosing

Subjects who are discharged from the hospital will be instructed to have the study medication (including empty bottles/units) with them at each visit. Compliance will be assessed based on remaining study drug as compared to what should have been taken and the subject diary where the subject will enter the details of dosing. Details of treatment including any missing dose will be recorded on the eCRF. Sites are encouraged to contact the medical monitor or Sponsor for concerns of compliance with the treatment regimen, especially for subjects who miss doses due to problems with tolerability.

13.0 Non-Study Treatments

13.1 Prior and Concomitant Medications

All medications (including prescription and over-the-counter medications, supplements, and herbal products) taken from 30 days before Baseline/Day 1 through TOC (Day 17) for VVC and EOT for all other fungal diseases will be recorded on the eCRF. Immunosuppressants (e.g.,

chemotherapy, corticosteroids, T-Cell immunosuppressants) used up to 90 days prior to subject enrollment will be recorded on the eCRF. Antifungal medications administered for the treatment of the eligible fungal infection if received for ≥ 7 days in the preceding 6 months prior to enrollment will also be recorded on the eCRF. In individual cases, timelines beyond 6 months or treatments less than 7 days may be requested for the record as clinically relevant, as judged by the Investigator and the Sponsor. Only the use of other antifungal medications, antibiotics for any reason or medications to treat an AE will be recorded after EOT (TOC for VVC subjects) and through the last observation in the study (35-Day FU for VVC, 6-Month FU for ABPA and 6-Week FU for all other fungal diseases). Start and stop times of concomitant medications taken during antifungal therapy will be recorded on the eCRF. Subjects will also record any new concomitant medications taken between visits in the subject diary.

See [Section 13.2](#) and [Section 13.3](#) for prohibited medications and medications to be administered with caution, respectively.

